### I. Hypotheses and Specific Aims:

Due to the success of combination antiretroviral therapy (ART), more than one-half of the estimated 1.2 million persons with human immunodeficiency virus-1 (HIV) in the United States are now age 45 or older[1]. Although they are living longer, current evidence suggests that persons with HIV infection have higher than expected rates of aging complications including physical function impairment, frailty, and falls[2-5]. The pathogenesis of aging complications in HIV, such as physical function impairment, is not well understood.

***Insulin-like growth factor (IGF)-I is the primary mediator of growth hormone (GH) effects on muscle and bone. Low IGF-I is associated with frailty, sarcopenia (low muscle mass and strength), and mortality in some aging cohorts.*** In our cohort of middle-aged HIV+ adults on effective ART, lower IGF-I was associated with a significantly greater odds of functional impairment [6]. Based on our data, we believe impairment in the GH/IGF-I axis may be an important pathway leading to aging complications in HIV. Early evidence of an HIV-GH interaction was illustrated in a rodent model where injection of the HIV envelope protein (gp120) into the hypothalamus suppressed GH[7]. GH deficiency is seen with lipodystrophy and GH resistance with AIDS wasting, but most studies of the GH/IGF-I axis in HIV+ persons are limited to: 1) cross-sectional analyses; 2) young subjects with wasting or lipodystrophy; 3) studies conducted prior to the era of combination modern ART treatment; 4) low numbers of women; and 5) significant subject and treatment heterogeneity. ***Little is known about the GH/IGF-I axis in the current era of HIV and ART, the role of GH/IGF-I in physical function in HIV, or the role of the GH/IGF-I axis on the aging trajectory in HIV.***

My long-term goal is to promote successful aging among persons with chronic HIV-1 infection by strategies to optimize physical function and minimize disability and frailty. The primary objective of this proposal is to investigate the GH/IGF-I axis as a potential pathway of early functional impairment in persons aging with HIV. My research is anticipated to advance understanding of the mechanisms and interactions of the GH/IGF-I axis in physical function. My central hypothesis is that a phenotype of accelerated functional impairment observed among some persons with HIV infection will be associated with disruption in the GH/IGF-I axis (the somatopause). This hypothesis will be evaluated through the following specific aim:

**Specific Aim 1: Determine the impact of high or moderate intensity combined resistance (REx) and cardiovascular exercise (CEx) on physical function in older HIV+ (n=36) and HIV- (n=36) adults.**

Approach: Previously sedentary older adults (aged 50-75 years) will undergo a 24 week REx + CEx exercise training intervention.

Hypothesis 1a: Both HIV+ and HIV- older adults will have a significant improvement in physical function (chair rise time) with REx + CEx, but HIV+ will have a *lower* increase than HIV- older adults.

Hypothesis 1b: Both HIV+ and HIV- older adults randomized to a high intensity REx + CEx intervention will have greater improvement in physical function than those randomized to the moderate intensity exercise.

Hypothesis 1c: Utilizing established techniques for screening and training, moderate intensity exercise followed by randomization to either continue a moderate- or progress to high- intensity exercise will result in minimal or no adverse events and will result in similar completion rates, with 80% of participants completing the training program.

**Specific Aim 2: Determine the impact of high or moderate intensity combined REx and CEx on local and systemic IGF-I, as an explanatory factor in the physical function changes of older HIV+ and HIV- adults.**

Approach: Previously sedentary older adults (aged 50-75 years) will undergo a 24 week REx + CEx exercise training intervention.

Hypothesis 2a: HIV+ older adults will have lower *systemic* IGF-I at baseline and at week 20 compared to HIV- adults, with blunted response to exercise training.

Hypothesis 2b: HIV+ older adults will have lower baseline and lower week 20 *skeletal muscle* IGF-I mRNA and IGF-I protein, compared to HIV- adults

**Specific Aim 3: Demonstrate a dose-response relationship between exercise intensity and chronic inflammation in HIV+ and HIV- adults aged 50 to 75 years.**

Hypothesis 3a: Older HIV+ adults will have a lower acute response to exercise (lower systemic IL-6 and TNF $\alpha$ ) at baseline and with 12 weeks training, in comparison to HIV- older adults.

Hypothesis 3b: Older HIV+ adults training on a high-intensity exercise regimen for 12 weeks will experience a greater initial increase in systemic IL-6 without a detrimental increase in TNF $\alpha$  in response to an acute bout of exercise, compared to those randomized to moderate-intensity exercise Hypothesis 3b: After 24 weeks of training, older HIV+ adults randomized to high-intensity exercise will experience a greater relative decline in chronic (resting) markers of systemic inflammation (IL-6, STNFRI, TNF $\alpha$ ) compared to those randomized to moderate-intensity exercise and compared to HIV- adults.

Specific Aim 4: Use qualitative methods to understand the barriers and facilitators to starting and maintaining an exercise program among older, HIV-infected population with multiple health disparities.

Hypothesis 1. Barriers to exercise will be identified among older HIV-infected men and women; these issues may focus around themes such as access to exercise facilities, body image, income/resources, stigma of HIV, and social support. Facilitators to routine physical activity and to continuation of exercise after completion of the exercise program will include greater exercise self-efficacy.

Methods: Focus group and individual interviews will be conducted among 1) participants who are currently exercising or who recently completed the exercise intervention study (K23 AG050260), or 2) participants not enrolled in the study. Participants will be men or women with HIV infection, aged 50 and older who are either exercising regularly or not exercising, similar to the recruitment criteria for the current participants. Semi-structured interviews for group interviews will be framed around the theoretical framework of behavior change, self-efficacy, and the Social Ecological Model.

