- Participants on anticoagulants (clopidogrel, Coumadin, etc) will be excluded from the muscle biopsy. Patients on short-acting anticoagulant therapy requiring dose cessation for only 48-72 hours (rather than 1-2 weeks for clopidogrel or Coumadin) for can be considered for muscle biopsy with approval by their hematologist or treating physician.
- Aspirin and Non-steroidal anti-inflammatory agents are not exclusions but should be stopped 1 week prior to biopsy.
- For the substudy only, participants experiencing a diarrheal change in bowel habits consisting of greater than one loose stool a day within the last two weeks will be excluded. Patients with chronic loose stools will be included.
- Focus Group Substudy will be more inclusive, as participants will only be participating in a group meeting and not exercising as part of the study:
  - Inclusion:
    - Age 50 or older at study entry
    - Either 1) currently exercising 2 days/week or more, or sedentary  $< 2$  days/week of CEx and/or REx over the prior 6 months
    - Willing to participate in a group discussion with other HIV-infected individuals
    - HIV-infected for at least 2 years.
  - Exclusion criteria:
    - Non-English speaker (group discussions will be in English only)
    - Unable to participate in any form of exercise. Participants with severe activity limitations will still be eligible, as they could still participate in balance training, band resistance, etc.
    - Unable to provide own consent.
    -

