9. Focus group discussions (main study and sub-study participants). Participants will be interviewed in a quiet conference room with round-table seating, located on the Anschutz Medical Campus for convenience. Focus group interviews will be conducted in group sessions, with up to 8-12 HIV-infected participants in each group. We estimate 3 group interviews with ~ up to 24 participants total for current exercise study participants, and up to 5 group interviews for HIV-infected participants not currently exercising (anticipate 6 group sessions: 1 noon and 1 evening meeting for women, 1 noon and 1 evening meeting for non-exercising men, 1 noon and 1 evening meeting for exercising men). Because recruitment for K23 AG050260 is targeting initial recruitment of HIV-infected participants, Aim 1 will focus on HIV-infected participants only. Interviews will be audio-recorded and will last up to 120 minutes. Additional individual interviews lasting 30-60 minutes with select participants (up to 8) with unique perspectives may be conducted. We will continue interviews until further interviews are felt unlikely to provide novel themes.

Risk: The main risk with the discussion groups is confidentiality.

Plan to minimize risk: Participants will have completed the full study consent prior to enrollment (if in the main study), and will complete an additional consent if interested in the qualitative assessments. All the data generated from the study will be kept strictly confidential. Group interviews will be conducted among HIV-infected participants only. Participants will be notified clearly in the consent and prior to scheduling the focus group sessions that all involved participants will be HIV-infected, and therefore their HIV status will be known to others. Participation within the focus groups will be entirely voluntary. All data will be collected using unique patient identification codes.

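### The only entry criteria for the Aim 4 qualitative work require willingness to join a group where HIV status becomes known, with no stated interview-only route, so stigma may be under-represented

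*Combined protocol and SAP*

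**What the plan says.** Specific Aim 4 in Section I gives the expected barriers in its Hypothesis 1: "these issues may focus around themes such as access to exercise facilities, body image, income/resources, stigma of HIV, and social support". Its methods paragraph names two kinds of data collection: "Focus group and individual interviews will be conducted among 1) participants who are currently exercising or who recently completed the exercise intervention study", and also among people not enrolled in the exercise study.

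Section IV.B (Description of Population to be Enrolled) ends with one eligibility list for this component. It is introduced by "Focus Group Substudy will be more inclusive, as participants will only be participating in a group meeting". Among its inclusion criteria is: "Willing to participate in a group discussion with other HIV-infected individuals".

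Section IV.D item 9 (Focus group discussions) names confidentiality as the main risk of the groups. It states "Group interviews will be conducted among HIV-infected participants only" and requires that people be told, in the consent and before scheduling, that "all involved participants will be HIV-infected, and therefore their HIV status will be known to others". Individual interviews appear in the same item in one sentence: "Additional individual interviews lasting 30-60 minutes with select participants (up to 8) with unique perspectives may be conducted".

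**The concern.** The component is meant to find out what keeps older adults with HIV from exercising, and stigma and social support are two of the five themes it names in advance. Entry depends on agreeing to sit in a group where each member's HIV status is known to the rest. Unwillingness to do that is plausibly related to stigma, and perhaps to isolation. If so, the sample is partly selected on a theme under study.

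At stake is what the transcripts can show. If stigma comes up rarely, the investigators could not tell whether it matters little in this population or whether some of the people it affects never entered. Nothing in the plan acknowledges this limit or collects the information needed to describe it.

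**Working it through.** No arithmetic applies: the point depends on no sample size, rate or effect size, and the plan gives no figure to reproduce. The check is to set the relevant sections side by side.

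1. **Is stigma a target of the work?** Yes, as an example. Aim 4 Hypothesis 1 lists HIV stigma and social support among five expected themes. Section II (Background) adds that support networks are often fragmented in this population.

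2. **Does entry depend on joining a group?** Yes, by the Section IV.B list. Its preamble describes taking part as attending a group meeting only, so it does not provide for someone who is interviewed alone. No second list exists.

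3. **Does joining a group disclose HIV status?** Yes. The criterion itself speaks only of willingness to take part in the discussion. The disclosure follows from Section IV.D item 9, which says it outright. Among group members, it is made only to other people with HIV.

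4. **Do the individual interviews offer another way in?** None is stated.
   - Aim 4 plans them without setting any entry condition.
   - Section IV.C item 10, which describes the conduct of this part, mentions the group meeting only.
   - Section IV.D item 9 describes the interviews as additional and optional, for selected participants with unusual perspectives. It does not present them as an alternative to a group.
   - The qualitative paragraph of Section F refers to both individual and group interviews but says nothing on eligibility.

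5. **Would the stopping rule reveal the gap?** No. Section IV.D item 9 continues interviews until new themes seem unlikely. That judgement is made within the people admitted and cannot show what those not admitted would have said.

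6. **Does this fit the stated purpose?** Only in part. The Background adds non-enrolled people partly to hear from those whom social barriers may have kept out of the exercise study. The justification under item 9 also wants to hear from people unable or uninterested in joining it. The substudy does widen entry: it has no upper age limit, it takes exercising or sedentary people, and it allows severe activity limitations. The group criterion narrows entry on a different dimension, one close to the social barriers mentioned.

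Steps 2 to 4 together give the result: for a person who declines the group, the documents state no route into the qualitative component.

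**The case against.** The strongest reply is that the Section IV.B criterion governs the focus groups and nothing else. Willingness to join a group is an almost unavoidable condition for a group meeting. The list never mentions individual interviews, Aim 4 plans them with no such condition, and item 9 does not confine the selected interviewees to people who attended a group. This stands to the extent that exclusion from the interviews is inferred from a single list and a missing alternative; no sentence imposes it. But if the sponsor intends people who decline a group to be interviewed, the plan does not say so, and the same edit is needed.

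A second reply is that disclosure is only to peers with HIV. Someone put off by stigma in a public gym might speak freely in such a group. That is fair. It may weaken the deterrent, but the plan itself treats the disclosure as serious enough to require notice twice.

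A third is that participation is voluntary and qualitative samples are purposive. Voluntariness protects the person but does not make the sample informative, and a purposive sample would normally seek out people affected by the expected themes.

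A reader might go further and infer that the people most affected by stigma are shut out altogether, or that silence on stigma will be reported as evidence that it is unimportant. The documents support neither. They hold no data on who would decline a group. Stigma is an illustrative theme, not a tested hypothesis. Section IV.A sets the objective as exploring barriers and facilitators, and Section F plans coding to identify themes, not to estimate how common they are. Group members may also raise stigma themselves.

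**Conclusion.** The concern holds in a limited form. As written, the plan selects participants for the Aim 4 qualitative work on a trait plausibly linked to one or two of its expected themes, and it states no entry route for people who decline a group for reasons of privacy or stigma. The likely consequence is under-representation of stigma and lack of social support, not their complete absence.

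The size cannot be given. The documents contain nothing on the proportion who would decline, and any percentage would be a guess. The conclusion rests on two assumptions: that the single eligibility list applies to the whole component, which is the plain reading but is not spelled out, and that reluctance to join a group is related to stigma or isolation, which is reasonable but undocumented. The effect is confined to this exploratory component. The randomised comparison of exercise intensity, the comparison by HIV status and the laboratory aims are untouched. The change is still worth making because it is specific, reduces the selection and uses interviews already planned.

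**What to change.** Three small edits:

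- **Section IV.B, Focus Group Substudy inclusion list:** replace the group criterion with *willing to take part in either a group discussion or an individual interview*, and adjust the preamble so that it no longer describes a group meeting only.
- **Section IV.D item 9:** state that people who decline the group are eligible for the individual interviews already planned (up to 8). The slots need not all be reserved for them; how to divide them is a sampling decision for the investigators.
- **Same item:** record how many people decline the group and the reason given, so that any remaining selection can be reported as a limitation.

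No interviews are added. The cost is a few words in the protocol, a short record of those who decline, and somewhat fewer of the 8 slots for other unusual perspectives.

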## II. Background and Significance:

**Complications of aging with HIV.** ART has dramatically extended the life expectancy of HIV-infected people. Longer life expectancy is changing the demographics of the HIV epidemic and by 2015 half of those living with HIV in the US will be 50 years or older[8]. In comparison to HIV-uninfected populations, HIV-infected persons, even when on effective ART, experience excess morbidity and mortality[9-11]. Persons on ART have early onset of aging complications including osteoporosis and fractures[12-14], impaired physical function[15-17], frailty[18-22], and falls[23]. Preservation of physical function is a cornerstone of geriatric medicine and will be essential in promoting successful aging among people with HIV.

HIV-infected persons are at risk for early development of frailty or a frailty-like syndrome, especially if not taking antiretroviral therapy or if CD4+ T-cell count is low[20-22, 24-26]. Measures of physical performance have identified greater than expected impairments in walking speed, balance, ability to rise from a chair and peak exercise capacity[16, 17] among middle-aged and older adults with HIV-infection. Impaired physical function may result in decreased quality of life, social isolation, nursing home placement, hospitalizations, and ultimately, higher mortality[27-30]. As preliminary data to support this proposal, we found that 38-53% of *middle-aged HIV-infected adults who have undetectable plasma HIV-1 RNA on ART in the Infectious Diseases Group Practice (IDGP) at the University of Colorado Hospital (UCH) have moderate to high physical function impairment*[31]. We found that physical function impairment was associated with significantly lower insulin-like growth hormone, lower lean muscle mass, and lower bone mineral density (BMD). Furthermore, although we did not find the IGF-I was

Table 1. Odds of poor performance on functional testing per 100 ng/mL $\downarrow$  in IGF-1

Variable	OR (95% CI)	P value
Frailty	2.5 (0.8, 7.9)	0.13
Grip	1.8 (0.5, 5.9)	0.35
Activity	3.1 (1.0, 9.3)	0.04
Fatigue	7.6 (2.0, 28.7)	0.003
Weight loss	1.6 (0.4, 7.0)	0.54
Slowness	2.3 (0.4, 14.2)	0.36
SPPB	3.2 (1.0, 10.2)	0.05
Chair rise	4.3 (1.3, 14.1)	0.02
Tandem	2.2 (0.5, 9.3)	0.30
Walk	4.7 (0.7, 34.0)	0.12

associated with frailty overall, we did find significant associations between IGF-I and chair rise time, a measure of lower extremity strength, self-reported physical activity, and fatigue (table). *Based on our findings in elderly HIV- populations, we hypothesize that impairment in the growth hormone (GH)/insulin-like growth factor (IGF)-I axis is an underlying, and potentially modifiable, component in this aging process.*

**GH/IGF-I axis in “normal” aging.** Regulation of the GH/IGF-I axis is complex: pulsatile secretion of GH is primarily regulated through hypothalamic GH-releasing hormone (GHRH) secretion and feedback through somatostatin and ghrelin. In “normal” aging, decreased hypothalamic release of GHRH results in a ~1% per year decline of GH levels after age 30, referred to as the “somatopause”[32, 33]. The decline in mean GH, GH pulse amplitude, and GH pulse frequency result in a subsequent decline in hepatic IGF-I production[34]. As a result, up to 30% of older adults could be considered GH-deficient by IGF-I levels[32]. IGF-I is considered one of the most important mediators of muscle and bone growth[35], and low systemic IGF-I has been associated with frailty[36, 37], slowed walking speed, decreased strength, and increased mortality[38, 39]. IGF-I is directly involved in the muscle adaption to exercise, and may explain, in part, impaired exercise tolerance seen in older individuals, or adults with HIV[16]. One of the most potent stimuli of GH release and subsequent skeletal muscle IGF-I production is acute exercise. The endogenous release is attenuated with age, obesity, poor sleep or nutrition[40, 41]. The impact of HIV on the endogenous release of GH/IGF-I is not known.

Therapies that target the GH/IGF-I axis have an anabolic effect on lean body mass (LBM) and bone mineral density (BMD). Shorter-term GH therapies ( $\leq 6$  months) typically result in increases in LBM without subsequent improvement in muscle function. However in studies of longer GH administration in GH-deficient adults (ie,  $>12$  months), increases in muscle strength are consistently found[42-46]. GH replacement over 5-10 years nearly normalizes muscle strength among GH deficient adults with low baseline LBM and strength[42, 47]. Whether the effect of GH/IGF-I-axis therapy on muscle function is sustained after cessation of therapy is unknown. GH replacement is also associated with improved aerobic capacity, lipid profiles, insulin sensitivity, and quality of life, suggesting that the effects of GH on physical function in GH deficient adults may be multifactorial[48-52]. Limited efficacy, expense, and adverse effects of continuous GH-axis replacement suggest that mitigating the decline in GH through enhanced endogenous release (i.e. exercise) or improved local response to IGF-I may be better strategies to maintain physical function.

**GH/IGF-I axis in HIV.** Many factors can contribute to alterations in the GH/IGF-I axis, but whether long-standing HIV infection is an independent risk is not clear. HIV proteins are present in the hypothalamus of deceased subjects with advanced HIV[53]. Injection of the HIV envelope protein (gp120) into the third ventricle of rodents suppressed GH secretion compared to saline, suggesting HIV may have a *direct* effect at the hypothalamic level[7]. A GH-resistant state is seen in AIDS patients, with or without wasting, with higher baseline GH but markedly lower IGF-I and/or IGFBP-3 levels compared to HIV- controls[54-57]. Conversely, lower basal GH, reduced pulsatility, and blunted response to exogenous GHRH but similar IGF-I was seen in HIV-associated lipodystrophy compared to HIV- controls[54, 58, 59]. Most of these studies were conducted  $>10$  years ago, and involved few women, few contemporary ART regimens, and few persons aged  $>50$  years. ***None of these studies investigated a potential association between GH/IGF-I and functional impairment or aging outcomes.***

Multiple mechanisms could explain the association between physical function and GH/IGF-I axis changes with age and HIV. First, little is known about the effect of different ART on the GH/IGF-I axis. In initial GH studies, HIV+ subjects were either untreated or on ZDV monotherapy. The largest study of the GH/IGF-I axis in HIV+ subjects (N=164) did not detect a difference in GH between the NRTIs and protease inhibitors, but individual ART drugs were not compared[60]. We are currently investigating the impact of ART in a different study to help answer this question. Second, the role of sleep in the GH-HIV relationship is unknown. Although GH secretion is circadian, the link between slow wave sleep and the GH/IGF-I axis is weak in most cohort studies[61-64]. Insomnia and/or other sleep disturbances, however, are very common and may be independently associated with HIV[65-70], and both low IGF-I and poor sleep are associated with physical function impairment[71-73]. Therapies targeting the GH/IGF-I axis among HIV+ persons (for lipodystrophy or wasting treatment), have resulted in increased LBM [74, 75] and gain in muscle function and exercise capacity[76, 77]. The newer GHRH analogue, tesamorelin, appears to be effective at decreasing central fat and increasing LBM with minimal side effects compared to prior GH therapies [78]. Among both HIV+ and HIV- persons, cessation of therapy almost inevitably reverses the LBM gain, supporting a role of the GH/IGF-I-axis in mediating physical function changes among aging, HIV+ adults[78, 79]. *Since low IGF-I, low muscle mass[80-82] and functional impairment are predictors of mortality and morbidity in both HIV-infected and -uninfected elderly[83-85], our findings of frequent low LBM and BMD in middle-aged HIV-infected persons raise concerns about potential risks for loss of independence as HIV-infected persons age.*

**Exercise as an intervention to promote successful aging.** In addition to the benefits on the GH/IGF-1 axis, the health benefits of regular physical activity for older adults are recognized by national and international organizations including the National Institute on Aging (Go4Life), the Agency for Healthcare Research and Quality (STEP Physical Activity Program), and the World Health Organization[86]. The Department of Health and Human Services- Physical Activity (DHHS-PA)

guidelines recommend that adults perform 150 min of moderate- or 75 min of vigorous-intensity endurance exercise (CEx) per week, and moderate-intensity resistance exercise (REx: i.e., weight training) on at least 2 days/week, to regularly stimulate the cardiorespiratory, musculoskeletal, and metabolic systems[87].

The DHHS-PA guidelines can be met by sedentary older adults or adults with chronic disease via progressive (i.e., incremental) CEx and REx exercise training methods. Exercise training interventions that combine CEx and REx are associated with improved physical function[88, 89], muscle strength[90], or both[91]. Beyond these direct effects of exercise, training-related improvement in physical function was associated with better quality of life (QoL)[90] and lower IL-6[92] in older adults. A greater reduction in inflammatory markers with exercise may result in greater improvement in muscle mass, strength, or exercise capacity among persons with chronic inflammation[93, 94].

Existing studies of exercise interventions among HIV-infected adults have primarily focused on gain in LBM among persons with wasting syndrome, or metabolic and cardiovascular benefits among persons with lipodystrophy. REx with or without additional interventions (e.g., testosterone, whey protein, carnitine) improves LBM in HIV-infected adults[95-100] while CEx improves insulin resistance, exercise capacity, and body composition changes associated with lipodystrophy[101-109]. Among HIV-infected adults, exercise interventions improved sit-stand time and short-walk speed[110] and increased 6-minute walk[111]. As in HIV-uninfected older adults, exercise or lifestyle modification reduces inflammatory markers in middle-aged HIV-infected individuals[104, 112].

**Exercise as an intervention to increase IGF-I.** Exercise is a potent stimulus of IGF-I production, although the effect appears to be most strongly mediated through the local production at the level of the muscle. Changes in *systemic* IGF-I with exercise are inconsistent across study populations[113], partly limited by variability in the type and intensity of exercise intervention. For example, changes in serum IGF-I with 6 months of cardiovascular exercise among 52 older, healthy adults did not result in significant changes in serum IGF-I, however, the intervention did not include REx[114]. In contrast, other studies have found increases in serum IGF-I with REx. More consistently, REx results in an increase in skeletal muscle IGF-I or IGF-I mRNA[115-118]. When skeletal muscle is subject to mechanical loading, two splice variants (IGF-IEa and MGF or IGF-IEc) are expressed. IGF-IEa isoform is expressed in both resting and working muscle and may serve more of an endocrine action similar to IGF-I production in the liver. In contrast, the MGF is more muscle specific, with autocrine or paracrine actions, and may be more involved in the early muscle repair and satellite cell activation. Similarly, IGF-IEa is thought to be more responsive to GH whereas MGF is relatively insensitive to GH[119, 120].

Of 28 post-op older adults were randomized to REx, nerve stimulation, or function exercises, only the REx arm had significant gain in both IGF-IEa and MGF as well as muscle fiber hypertrophy. These findings suggest that routine physical activity or rehabilitation focused on functional improvement alone is not enough to overcome the sarcopenia found in many older adults[121]. Furthermore, in a recent publication, 15 men with abdominal obesity treated with rhGH for 12 weeks experienced an increase in both skeletal muscle mRNA and serum IGF-I, with serum changes associated with improvements in body composition and muscle mRNA associated with changes in skeletal muscle mitochondrial function, suggesting differing mechanisms between systemic and local IGF-I[122]. The increase in IGF-I mRNA and protein is blunted with aging, but the impact of HIV on the ability to respond to the exercise stimulus is not known. Further examples of the impact of REx, CEx or both on IGF-I are shown in the table below.

	Cohort	Intervention	Outcome	Notes
Vitiello, [114]	67 healthy older adults	CEx x 6 mo	Serum IGF-I (No difference)	
Hameed [118]	19 healthy 74 y/o men	REx, GH or REx + GH	All groups had increase in mRNA IGF-1, GH alone increased IGF-IEa, but MGF was enhanced with REx added	No change in serum IGF-I with REx alone -REx also increased IGF-IEb
Hameed [117]			Young subjects had increase in MGF but not IGF-IEa mRNA 2.5 h after single-bout exercise; older adults did not	
Singh[123]	Older men & women	10 wks REx	500% increase in IGF-I within muscle but did not distinguish isoforms	
Kim[124]	20 young and 18 older adults	1x REx	IGF-IEa increased 34%; detected a load and age interaction with an increase of only 16% among older adults	
Hambrecht[125]	18 with CHF	½ to EX, ½ to none	Increase in IGF1 at muscle, decrease in IGFR at muscle	Systemic IGF-1 fails to respond to GH stimulus with disease,

				suggesting peripheral GH resistance not overcome with ex
Bamman[116]	10 healthy subjects (mean age 24 years)	8 sets concentric or eccentric REx	Single bout of mechanical loading increased IGF-1 mRNA by 62% and were greater in eccentric group	
Gregory[126]	Healthy women	8 weeks REx, CEx, or both	8 weeks of R or R+E increased total IGF and decreased IGFBP-1	
Kraemer [127]	8 younger, 9 older men, all physical active but no REx	REx 3x/wk x 10 weeks	Exercise induced increases in T were more pronounced in younger, IGF didn't change with EX	
Lovell [128]	32 older men	12 REX, 12 AEX, 12 control to 16 weeks	No differences in serum GH, IGFI, testos, SHBG, FT, but did have transient T elevation immediately after REx	

